#### 5 Introduction and trial rationale

#### 5.1 Chronic hand eczema

Chronic hand eczema (CHE) is a serious inflammatory skin disorder located anywhere on the hands or wrists. In the acute stage, it is clinically characterised by erythema, infiltration, oedema, or vesicles, and in the chronic stage by scaling, fissures, and hyperkeratosis, and the condition may be exacerbated by bacterial infections. Important symptoms include itch and pain, and the disease is often characterised by relapses and a poor prognosis.

CHE refers to hand eczema which persists for more than 3 months or returns twice or more often within 12 months (1).

Hand eczema aetiology is usually multifactorial, and it is generally agreed that no simple relationships exist between clinical patterns and aetiological diagnoses (2). Several different classifications have been proposed (1, 3, 4), however it is generally agreed that the most common subtypes of CHE are contact dermatitis (irritant and allergic), atopic hand eczema, and hyperkeratotic eczema (5). Other subtypes include acute recurrent vesicular hand eczema, and contact urticaria/protein contact dermatitis (1).

The reported prevalence and incidence rates of hand eczema vary considerably, depending on the methodology in the collection of data. In a review of data available from 1964 to 2007, the prevalence of hand eczema in the general population was approximately 4%, 1-year prevalence about 10%, and life-time prevalence approached 15% (6). In another study by Thyssen et al. (7), approximately 7–10% of patients with hand eczema reported symptoms 'nearly all the time', implying a chronic state of the disease. Based on data from 7 studies, the incidence rate of hand eczema was 5.5 cases/1000 person-years with a higher median incidence rate among women (1). Several risk factors, such as pre-existing atopic dermatitis (AD), female sex, wet work, and contact allergy have been identified (6, 8). The prevalence of hand eczema is different across age groups (6) with a mean/median first onset in the early or mid-20'ies (9-11). However, approximately one-third of men and women report their first hand eczema before the age of 20 (12).

The socioeconomic burden of CHE is significant. 5 studies from 4 countries have found that total societal costs (direct and indirect) ranged between USD \$1,924 and USD \$8,212 (inflated to 2017 cost) per patient per year (1, 13-16). CHE is associated with increased sick leave (17, 18) as well as job loss and change in jobs (5, 19, 20). Overall, CHE has a

Page 26 of 121

significant detrimental effect on health-related quality of life (HRQoL), work productivity, daily activities, and health care costs (13).

Although the molecular mechanisms underlying CHE are not fully understood, a large panel of cytokine-mediated signalling cascades have been identified as part of the pathophysiology, including cytokine responses representing Th2 pathway (IL-4, IL-13), Th22 pathway (IL-22), Th17 pathway (IL-17), Th1 pathway (interferon-γ), and the JAK/STAT (janus kinase/signal transducer and activator of transcription) pathway. As the JAK proteins are required for signalling of most cytokines, blocking of JAKs reduces cytokine signalling and thereby abrogates the vicious cycle that leads to the development of CHE (21-23).

CHE is generally difficult to treat and presents with periods of flares and periods of remissions. Long-term disease control of CHE may require reactive treatment of flares and proactive treatment for the prevention of flares.

Treatment of CHE involves different disease management strategies such as elimination of triggers, general skin care, and anti-inflammatory therapy in a step-wise approach. General skin care in terms of emollients is widely used and recommended by physicians, but evidence of efficacy is sparse (1). Elimination of triggers such as allergens and irritants is a necessary prerequisite for successful therapy on a longer term. Topical corticosteroids (TCS) remain the mainstay of topical anti-inflammatory therapy for hand eczema. However, long-term use of TCS is restricted due to side effects such as skin atrophy and potential inhibition of skin barrier repair (24).

Whereas mild CHE to some extent may be managed by elimination of triggers, general skin care, and TCS, management of moderate to severe CHE is more cumbersome. Alitretinoin (25) is the only approved product specifically indicated for treatment of CHE but is only indicated for severe CHE unresponsive to treatment with potent TCS, and only approved in Europe and a few other countries worldwide.

Considering the paucity of approved therapies for the treatment of CHE, other therapeutic options are limited to those approved for other skin diseases with an inflammatory pathophysiology. These applied treatments lack the clinical documentation for use in CHE.

As the currently available treatment options either lack documented treatment effect or are limited by restrictions of long-term use due to safety concerns (1, 26), there is a high unmet medical need for new topical treatment of moderate to severe CHE with high efficacy in combination with a good safety profile especially for long-term use. New and better treatments would potentially improve HRQoL of patients with moderate to severe CHE.

Page 27 of 121

Delgocitinib has the potential to address the unmet medical need associated with this burdensome disease.

# 5.2 Experience with investigational medicinal product

Delgocitinib (LEO 124249) is a pan-JAK inhibitor, which blocks various cytokine-mediated signalling pathways and widely suppresses the activation of immune and inflammatory cells such as T-cells, B-cells, mast cells, and monocytes activated by these cytokines (27).

In nonclinical studies, topically administered delgocitinib inhibited inflammation in rat and mouse AD- and psoriasis-like models of contact dermatitis and reduced IL-31-induced scratching in mice. Topical administration of delgocitinib was also shown to improve the impaired skin barrier function in mouse models and in human skin (28).

The efficacy and safety of delgocitinib in CHE has been demonstrated in a phase 2a trial (LP0133-1180) with delgocitinib ointment 30 mg/g and in a phase 2b dose-ranging trial (LP0133-1273) with delgocitinib cream (1, 3, 8, and 20 mg/g).

In the LP0133-1180 trial, delgocitinib ointment 30 mg/g was applied twice daily for 8 weeks in adult subjects with mild to severe CHE. A statistically significant difference between delgocitinib ointment 30 mg/g and ointment vehicle was observed for the primary endpoint: Physician's Global Assessment (PGA) treatment success at Week 8 (defined as achieving a PGA score of 0 [clear] or 1 [almost clear] with a  $\geq$ 2-step reduction from baseline).

In the phase 2b dose-ranging trial (LP0133-1273), delgocitinib cream (1, 3, 8, or 20 mg/g) was applied twice daily for 16 weeks in adult subjects with mild to severe CHE. For the 2 highest doses of delgocitinib cream (8 mg/g and 20 mg/g), a statistically significant treatment effect was observed in terms of Investigator's Global Assessment for CHE treatment success (IGA-CHE TS) at Week 16 (defined as achieving an IGA-CHE score of 0 [clear] or 1 [almost clear] with a ≥2-step reduction from baseline) and change from baseline in Hand Eczema Severity Index (HECSI) score at Week 16 compared with cream vehicle. For the dose and population selected for the present trial (delgocitinib cream 20 mg/g and subjects with moderate to severe CHE), 39.0% of subjects achieved IGA-CHE TS at Week 16 vs. 10.5% in the cream vehicle group (p<0.05) (29).

In both trials and for all doses, delgocitinib was well tolerated, and a low systemic exposure to delgocitinib was observed.

Page 28 of 121

Based on currently available nonclinical and clinical data, delgocitinib has the potential to become a novel local-acting anti-inflammatory and immunomodulatory agent for topical treatment of CHE, with skin-barrier-improving properties and a favourable safety profile.

#### 5.3 Trial rationale

This is a long-term extension trial to evaluate the long-term safety of an as-needed treatment with twice-daily applications of delgocitinib cream 20 mg/g in accordance with the ICH E1 guideline (30).

Subjects eligible for this trial will have received blinded treatment with either twice-daily delgocitinib cream 20 mg/g or cream vehicle and will have completed the 16-week treatment period in one of the 2 parent trials: LP0133-1401 or LP0133-1402.

The purpose of the parent trials is to confirm efficacy and evaluate safety of twice-daily delgocitinib cream 20 mg/g compared with cream vehicle for a treatment period of 16 weeks in adult subjects with moderate to severe CHE. Subjects transferring from the blinded parent trials will enter this extension trial without their individual treatment allocation being revealed, in order to maintain the blinding of the ongoing parent trial.

An open-label trial design is chosen as the aim of this trial is to evaluate the long-term safety of an as-needed treatment with twice-daily applications of delgocitinib cream 20 mg/g to mimic the anticipated use of delgocitinib cream in clinical practice. Further, a vehicle arm is not included since vehicle treatment beyond 16 weeks is not considered ethical.

Based on the available nonclinical and clinical data, delgocitinib cream has the potential to become an effective and well tolerated treatment for CHE and thereby improve HRQoL of affected patients.

#### 5.4 Ethical considerations

This trial will be conducted in accordance with the ethical principles that have their origins in the Declaration of Helsinki (31), the ICH GCP (32) guidelines, in compliance with the approved protocol, and applicable regulatory requirements.

The trial design chosen is regarded as scientifically justified and adheres to ethical standards that ensure the rights, safety, and well-being of the trial subjects. All subjects will be treated with open-label delgocitinib cream 20 mg/g twice daily as needed. All subjects will have previously participated in one of the parent trials.

Page 29 of 121

Subjects may initiate rescue treatment at the discretion of the investigator if medically necessary, in which case treatment with delgocitinib cream 20 mg/g will be discontinued immediately (see Section 9.5).

Pregnant or breastfeeding women and women trying to become pregnant will not be included in the trial. Women of childbearing potential must agree to use an acceptable birth control method to prevent pregnancy during the trial.

The subject's right to withdraw from the trial or discontinue IMP at any time is ensured. If subjects are withdrawn from the trial, they will be treated at the investigator's discretion or referred to other physician(s) according to standard practice.

In accordance with the current version of ICH GCP, qualified medical personnel employed/contracted by LEO Pharma will be readily available to advise on trial-related medical questions. Medical monitoring will be performed throughout the trial.

#### 5.5 Benefit/risk assessment

There is a clear unmet medical need for new long-term therapies for subjects with moderate to severe CHE. The only currently approved treatment option indicated for patients with CHE is alitretinoin, which is associated with significant safety precautions and is only indicated for severe CHE. Alitretinoin is only approved in Europe and a few countries worldwide.

Delgocitinib is a topically applied JAK inhibitor. Systemic JAK inhibitors are associated with potential adverse reactions and a black box warning concerning the risk of serious infections, malignancy, and thrombosis. These risks are not considered relevant for delgocitinib cream due to the very low systemic exposure observed in previous trials with topically applied delgocitinib.

No specific adverse drug reactions or important identified risks have been identified for delgocitinib cream during the nonclinical and clinical development to date. Nevertheless, as observed with other topical therapies, local skin reactions, such as pain (burning and stinging), sensitisation to IMP, allergic and irritant contact dermatitis, local immunosuppression, and skin infections, may occur. A detailed overview of nonclinical and clinical data on delgocitinib is available in the current investigator's brochure (33).

The risk to subjects in this trial will be minimised by fulfilment of all eligibility criteria and by close clinical monitoring. To ensure the safety and wellbeing of subjects participating in this trial, safety will be monitored during the trial, and stopping criteria have been defined (Section 10.2).

Page 30 of 121

The blood sampling procedure poses the same low risk as normally associated with this procedure (i.e. infection, bleeding into the surrounding tissue, and, very rarely, inflammation of the vein or formation of blood clots). Blood sampling will be conducted by qualified medical personnel.

Altogether, the risks associated with participating in this clinical trial are considered low and are expected to be outweighed by the benefit of a potential future treatment option for CHE.

Participation in clinical trials may currently be associated with increased risk and added challenges due to the COVID-19 pandemic caused by SARS-CoV-2. The proposed trial is not believed to put subjects with CHE at an increased risk for viral infections including SARS-CoV-2. However, a risk of exposure to infected people cannot be excluded as the trial subjects may enter public areas (e.g. commute to the trial site) and have additional human contact (e.g. with trial site staff). Appropriate risk assessments and mitigation measures must be considered to protect the subjects and trial site staff and to ensure the integrity of the trial data. It is unknown whether treatment with delgocitinib cream 20 mg/g may predispose to COVID-19, but ongoing safety monitoring will ensure that all adverse events are continuously monitored.

The EMA (34), FDA (35), and national health authorities in Europe and Canada have issued new guidelines that aim to provide recommendations for conduct of clinical trials during the COVID-19 pandemic. Given the circumstances of the potentially relapsing pandemic situation with regard to the spread of COVID-19 in the future, special attention will be paid to protecting subjects participating in the trial and site staff involved in the investigations against infection with SARS-CoV-2 as requested by the EMA guideline.

Page 31 of 121

During the trial, the investigators will be trusted to take appropriate actions to ensure the safety of the individual subjects according to local authority-issued preventive measures. As these can differ across countries and regions, no general instruction from the sponsor can be provided concerning subject safety and the need for postponing trial visits. In case of local authority-issued preventive measures, the investigator can convert on-site visits into phone or video consultations. At phone/video visits, no investigator assessments of efficacy can be done. Therefore, if and only if subjects are prevented from attending on-site visits due to local authority-issued preventive measures, a decision to start or stop treatment with delgocitinib 20 mg/g can be taken based on a phone or video visit. Safety monitoring remains an obligation to LEO Pharma, and it is considered feasible to collect safety data remotely (via electronic communication) where on-site visits are not possible. Other mitigating measures include collecting patient-reported outcome (PRO) data via a web-based solution and ensuring supply of IMP to the subjects to overcome local authority-issued preventive measures due to the COVID-19 pandemic (see Appendix 7 for details).

### 6 Trial objectives and endpoints

Panel 3: Objectives and endpoints

Objectives	Endpoints
Primary objective	Primary endpoint
To evaluate the long-term safety of an as-needed treatment with twice-daily applications of delgocitinib cream 20 mg/g.	Number of treatment-emergent AEs from baseline up to Week 38.
Secondary objective	Secondary endpoints
To evaluate the long-term efficacy of an as-needed treatment with twice-daily applications of delgocitinib cream 20 mg/g.	
 
IGA-CHE score at each scheduled visit from baseline up to Week 36.
 
IGA-CHE score of 0 (clear) or 1 (almost clear) at each scheduled visit from baseline up to Week 36.
 
HECSI score at each scheduled visit from baseline up to Week 36.
 
HECSI-75 at each scheduled visit from baseline up to Week 36.
 
HECSI-90 at each scheduled visit from baseline up to Week 36.
 

Other/exploratory objectives	Other/exploratory endpoints
To explore efficacy, health-related quality of life, and work productivity for an as-needed treatment with twice-daily applications of delgocitinib cream 20 mg/g.	
 
Efficacy
 
Number of days on treatment with delgocitinib cream 20 mg/g from baseline up to Week 36.
 
Number of on-treatment periods² from baseline up to Week 36.
 

Page 32 of 121

Objectives	Endpoints
	
 
Proportion of response days from baseline up to Week 36.
 

	
 
Mean duration of on-treatment periods per subject from baseline up to Week 36.
 

	
 
Time to first IGA-CHE score ≥2 in subjects previously treated with delgocitinib cream 20 mg/g in the parent trial and who achieved IGA-CHE TS at Week 16 in the parent trial.
 

	
 
Time to first response (IGA-CHE score of 0 [clear] or 1 [almost clear]) in subjects who did not achieve IGA-CHE TS at Week 16 in the parent trial.
 

	• Time to response (IGA-CHE score of 0 [clear] or 1 [almost clear]) following treatment re-initiation after first off-treatment period in subjects previously treated with delgocitinib cream 20 mg/g in the parent trial.
	
 
HESD score (weekly average) at each nominal week from baseline up to Week 36.
 

	
 
HESD itch, pain, cracking, redness, dryness, and flaking scores (weekly averages) at each nominal week from baseline up to Week 36.
 

	
 
Reduction of HESD score, HESD itch score, and HESD pain score, (weekly averages) of ≥4 points from parent baseline at each nominal week from baseline up to Week 36.
 

	Health-related quality of life
	
 
HEIS score at each scheduled visit with assessment from baseline up to Week 36.
 

	
 
HEIS (each individual domain) score at each scheduled visit with assessment from baseline up to Week 36.
 

	
 
DLQI score at each scheduled visit with assessment from baseline up to Week 36.
 

	
 
EQ-5D-5L visual analogue score at each scheduled visit with assessment from baseline up to Week 36.
 

	
 
EQ-5D-5L index score at each scheduled visit with assessment from baseline up to Week 36.
 

	
 
WPAI:CHE domain scores at each scheduled visit with assessment from baseline up to Week 36.
 

	Exposure and treatment compliance
	
 
Total amount of delgocitinib cream 20 mg/g used during the trial.
 

	Percentage of missed applications.

- 1. In the derivation of HECSI-75 and HECSI-90 the baseline score from the parent trials will be used.
- 2. An on-treatment period is defined from the day treatment is re-initiated (when IGA-CHE score ≥2 is observed by the investigator) to the day treatment is stopped (when IGA-CHE score of 0 [clear] or 1 [almost clear] is observed by the investigator).
- 3. Number of response days (days when a subject is not on treatment with delgocitinib cream 20 mg/g) divided by number of days between baseline and end of trial.

Page 33 of 121

4. Response days are defined as the sum of days where the subject is in response periods. A response period is defined as the period from the day IGA-CHE score of 0 (clear) or 1 (almost clear) is observed by the investigator, to the day IGA-CHE score ≥2 is observed by the investigator.

5. Among subjects with a parent baseline HESD score, HESD itch score, and HESD pain score (weekly averages) ≥4 points, respectively

Abbreviations: AE = adverse event; DLQI = Dermatology Life Quality Index; EQ-5D-5L = EuroQol 5-Dimension Health Questionnaire 5 Level; HECSI = Hand Eczema Severity Index; HECSI-75 = at least 75% improvement in HECSI score from baseline; HECSI-90 = at least 90% improvement in HECSI score from baseline; HEIS = Hand Eczema Impact Scale; HESD = Hand Eczema Symptom Diary; IGA-CHE = Investigator's Global Assessment for chronic hand eczema; IGA-CHE TS = IGA-CHE treatment success, i.e. an IGA-CHE score of 0 (clear) or 1 (almost clear) with a ≥2-step improvement from baseline; TS = treatment success; WPAI:CHE = Work Productivity and Activity Impairment: Chronic Hand Eczema.

Page 34 of 121

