#### Treatment period (Week 0 up to Week 36)

#### **Definition of terms:**

**Response** is defined as IGA-CHE score of 0 (clear) or 1 (almost clear).

Treatment re-initiation is triggered by an IGA-CHE score of  $\geq 2$  after having achieved IGA-CHE 0 (clear) or 1 (almost clear) in this trial.

At baseline (Day 1), subjects will be evaluated by the investigator to determine the severity of their CHE. Subjects with IGA-CHE score of 0 (clear) or 1 (almost clear) will not be assigned treatment with delgocitinib cream 20 mg/g; they will however continue to use their routine skin care emollient, if applicable. Subjects with IGA-CHE score ≥2 will start treatment with twice-daily delgocitinib cream 20 mg/g. Treatment will continue until IGA-CHE score of 0 (clear) or 1 (almost clear) is achieved.

If a subject experiences worsening of CHE signs and symptoms while off-treatment, the subject should contact the trial site. If a scheduled visit is not planned within a reasonable timeframe, an unscheduled visit should be planned as soon as possible. If an IGA-CHE score  $\geq 2$  is attested, the subject will be dispensed delgocitinib cream 20 mg/g and the investigator will instruct the subject to start treatment with twice-daily applications. The minimal set of assessments to be performed at an unscheduled visit to decide if treatment with delgocitinib cream 20 mg/g should be re-initiated is IGA-CHE and collection of AEs.

While on treatment with delgocitinib cream 20 mg/g, if the subject observes that CHE signs and symptoms are resolved, they should contact the trial site. If a scheduled visit is not planned within a reasonable timeframe, an unscheduled visit should be planned as soon as

Page 36 of 121

possible. If IGA-CHE score of 0 (clear) or 1 (almost clear) is achieved, the subject will be instructed to stop treatment and return all opened and unopened tubes to the site. The minimal set of assessments to be performed at an unscheduled visit to decide if treatment with delgocitinib cream 20 mg/g should be stopped is IGA-CHE, collection of AEs, and investigator's assessment of local tolerability.

For all subjects, regardless if on- or off-treatment, IGA-CHE will be evaluated by the investigator at visits to the trial site every 4 weeks from baseline up to Week 36.

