# 9.2 Administration of investigational medicinal products

Delgocitinib cream 20 mg/g will be administered as a twice-daily topical application, as needed (see Section 7.1). The applications will be performed approximately 12 hours apart. Instructions for use will also be provided.

Delgocitinib cream 20 mg/g will be applied to clean, dry hands, fingers, fingertips, and wrists in a thin layer covering the affected areas. The amount of delgocitinib cream 20 mg/g to be used depends on the size of the affected area and the size of the hands, fingers, fingertips, and wrists. 1 tube of 15 g delgocitinib cream is considered sufficient for treatment of the whole surface of the hands, fingers, fingertips, and wrists twice daily for 1 week; however, a few patients may need more (based on experience from the LP0133-1273 trial), which will be allowed at the discretion of the investigator.

Page 42 of 121

Prior to the first application of delgocitinib cream 20 mg/g and each time treatment is re-initiated, the subject will be instructed on how much cream to apply and which area(s) to treat.

Only the affected area(s) on the hand(s), finger(s), fingertip(s), and wrist(s) will be treated. If new CHE lesions occur on initially untreated area(s) of the hand(s), finger(s), fingertip(s), and wrist(s), these new lesions will be treated with delgocitinib cream 20 mg/g as well.

At the scheduled trial visits, investigator assessments of efficacy should preferably be done at least 2 hours after application of delgocitinib cream 20 mg/g or emollient. Recommendations for bathing, washing, and hand sanitising in relation to delgocitinib cream 20 mg/g application are provided in Section 9.6.

Tubes of delgocitinib cream 20 mg/g will be dispensed by the investigational staff if it is decided during a visit (scheduled or unscheduled) that a subject should start treatment. After that, delgocitinib cream 20 mg/g tubes will be dispensed to the subject at each scheduled visit until it is decided that the subject should stop treatment. Application of delgocitinib cream 20 mg/g will be recorded by the subjects each day in the eDiary.

Returned opened tubes of delgocitinib cream 20 mg/g will be weighed at the trial site to determine the amount of cream used. Subjects must return all previously dispensed tubes of delgocitinib cream 20 mg/g to the site at all visits (scheduled and unscheduled). For details on handling of unopened tubes, see Section 9.8.3.

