# 14.3.3 Exposure and treatment compliance

Based on the attended visits data, exposure to treatment will be presented for the safety analysis set as days of exposure during the trial.

The total amount of IMP used during the trial will be summarised for the safety analysis set.

Treatment compliance will be presented for the safety analysis set as the percentages of missed applications during on-treatment periods, derived from the eDiary.

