## 14.3.6 Analysis of other/exploratory endpoints

All analyses are based on safety analysis set.

The number of on-treatment days from baseline up to Week 36 will be summarised.

The number of on-treatment periods from baseline up to Week 36 and the rates per 100 person years of observation time will be presented.

The proportion of response days (days with IGA-CHE 0 or 1) from baseline up to Week 36 will be summarised. Mean duration of on-treatment periods per subject from baseline up to Week 36 will be summarised.

Time to first IGA-CHE score ≥2, initiation of rescue treatment, or discontinuation of IMP, whichever occurs first, will be presented for the subjects in the safety analysis set who were previously treated with delgocitinib cream 20 mg/g twice daily in the parent trial and achieved IGA-CHE TS at Week 16 in the parent trial. Kaplan-Meier curve and estimates will be presented. Subjects will be censored at the date of the last assessment visit in case of no events. Follow-up time to first IGA-CHE score ≥2 starts from the baseline visit.

Time to first response (IGA-CHE 0 or 1) will be presented for the subjects in the safety analysis set who did not achieve IGA-CHE TS at Week 16 in the parent trial, by treatment group assigned in the parent trial (delgocitinib cream 20 mg/g or cream vehicle respectively). Kaplan-Meier curves and estimates will be presented. Subjects will be censored at the date of the last assessment visit, initiation of rescue treatment, or discontinuation of IMP, whichever occurs first. Follow-up time to first response will be derived from the baseline visit.

Time to response (IGA-CHE 0 or 1) following treatment re-initiation after first off-treatment period will be presented for subjects in the safety analysis set who were treated with delgocitinib cream 20 mg/g twice daily in the parent trial. Kaplan-Meier curves and estimates will be presented. Subjects will be censored at the date of the last assessment visit, initiation of rescue treatment, or discontinuation of IMP, whichever occurs first. Follow-up time to response will be derived from the visit of treatment re-initiation after first off-treatment period.

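### Panel 3 opens an on-treatment period only at re-initiation, so read literally the first course of every subject entering with IGA-CHE ≥2 is not counted

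*Combined protocol and SAP*

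**What the plan says.** Section 6, Panel 3, footnote 2 gives the only formal definition: "An on-treatment period is defined from the day treatment is re-initiated (when IGA-CHE score ≥2 is observed by the investigator"). The period runs "to the day treatment is stopped (when IGA-CHE score of 0 [clear] or 1 [almost clear] is observed by the investigator"). In Panel 3 the marker for this footnote sits on the number of on-treatment periods.

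Section 7.1, under its definition of terms, makes re-initiation depend on an IGA-CHE score ≥2 "after having achieved IGA-CHE 0 (clear) or 1 (almost clear) in this trial". The next paragraph covers subjects not controlled at entry: "Subjects with IGA-CHE score ≥2 will start treatment with twice-daily delgocitinib cream 20 mg/g". It does not call this re-initiation. Section 9.2 likewise keeps the two events apart when it says instruction is given "Prior to the first application of delgocitinib cream 20 mg/g and each time treatment is re-initiated". Footnote 10 to Panel 2 does the same.

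The term is then used in the analysis sections:
- Section 14.3.6: "The number of on-treatment periods from baseline up to Week 36 and the rates per 100 person years of observation time will be presented".
- Section 14.3.6: "Mean duration of on-treatment periods per subject from baseline up to Week 36 will be summarised".
- Section 14.3.3 presents compliance as "the percentages of missed applications during on-treatment periods, derived from the eDiary".

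Sections 7.1 and 9.2 also use the term in a wider sense. Both speak of a continuous on-treatment period of 16 weeks without improvement and do not limit it to re-initiated courses.

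**The concern.** The trial describes how much cream people use under an as-needed regimen. A count of treatment courses that leaves out the first course of subjects who enter with active disease would not describe that. Taken together, footnote 2 and Section 7.1 have this effect: a Day 1 start is an initiation, and only re-initiations open a period.

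The omission is systematic. It falls on everyone with IGA-CHE ≥2 at baseline and on nobody else by the same route. A subject with one long course and no relapse would contribute no period and no mean duration. Compliance would lose the same courses if Section 14.3.3 applies the defined term. Two programmers working from this text could also produce different tables, one following the footnote and the other following the ordinary use of the term.

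**Working it through.** The plan states no figure that depends on this definition, so there is nothing to reproduce. The check has three parts.

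**1. Logic.** A period opens at re-initiation (Panel 3, footnote 2). Re-initiation needs an earlier IGA-CHE 0/1 in this trial (Section 7.1). A subject with IGA-CHE ≥2 on Day 1 has no earlier score in this trial. The Day 1 course therefore opens no period, and nothing else in Sections 6, 7 or 14 restores it. For subjects who enter at 0/1, it is unclear whether the baseline score counts as achieved in this trial. They are left out here.

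**2. Effect on individual subjects.** These are illustrative courses on the scheduled visit days of Panel 2, all with IGA-CHE ≥2 at baseline. Duration is stop day minus start day. For the first row, the Week 36 visit is assumed to close the course.

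| Course | Literal definition | Every course counted |
|---|---|---|
| Never responds (Day 1 to 253) | 0 periods, mean undefined | 1 period, 252 days |
| Response Week 12, no relapse (Day 1 to 85) | 0 periods, mean undefined | 1 period, 84 days |
| Response Week 8, relapse Week 16, response Week 24 (Day 1 to 57, 113 to 169) | 1 period, mean 56 | 2 periods, mean (56 + 56)/2 = 56 |
| Response Week 16, relapse Week 24, response Week 28 (Day 1 to 113, 169 to 197) | 1 period, mean 28 | 2 periods, mean (112 + 28)/2 = 70 |
| Response Week 4, relapse Week 12, response Week 24 (Day 1 to 29, 85 to 169) | 1 period, mean 84 | 2 periods, mean (28 + 84)/2 = 56 |

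The count is always one too low. The mean duration can be too low, unchanged, too high or undefined.

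**3. Size of the group.** Inputs:
- About 600 subjects are expected, from 920 in the parent trials (Section 14.1).
- Phase 2b Week 16 treatment success was 39.0% on 20 mg/g and 10.5% on vehicle (Section 5.2).
- The parent population has moderate to severe disease (Section 5.3). A score of 0/1 is then also a two-step improvement, so 1 minus the success rate is the share at IGA-CHE ≥2.
- The documents do not give the parent allocation ratio, so it is varied as an assumption.

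(a) If the phase 2b rates hold among those who roll over, with w the share from delgocitinib: 600 × [1 − (0.390w + 0.105(1 − w))].
- 1:1: 600 × 0.7525 ≈ 451
- 2:1: 600 × 0.705 = 423
- 3:1: 600 × 0.68125 ≈ 409

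(b) If every responder among the 920 rolls over: 600 − 920 × [0.390w + 0.105(1 − w)].
- 1:1: 600 − (179 + 48) ≈ 372
- 2:1: 600 − (239 + 32) ≈ 329
- 3:1: 600 − (269 + 24) ≈ 307

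Across these cases the share runs from 307/600 = 51% to 451/600 = 75%.

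**The case against.** The best reply is that this is a slip in one word. The parenthesis in footnote 2 names an observed IGA-CHE score ≥2 as the trigger, and a Day 1 starter meets it. Section 14.3.6 counts periods from baseline, and Sections 7.1 and 9.2 use the term for any course. That is a fair account of the likely intention. A reader might infer that the sponsor means to discard first courses, and the documents do not support that. The definition as written still gives the wrong count.

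Four stronger inferences should also be resisted.

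- *A continuous user would be recorded with no on-treatment days.* The number of days on treatment is a separate Panel 3 endpoint without the footnote 2 marker, and Section 14.3.6 does not say it is summed over periods. Footnotes 3 and 4 point the other way: a subject who never clears has no response days, and response days are the days off treatment.
- *AEs in first courses would be tabulated as off treatment.* Section 14.3.8.1 says only that status comes from IGA-CHE data. The amendment summary gives alignment with the on-treatment period as the reason, but no section says footnote 2 is the rule.
- *366 to 537 subjects bounds the group.* Those figures, 600 × 0.610 and 600 × 0.895, need all subjects to come from one parent arm. They also ignore that roll-over subjects are completers without rescue (Sections 8.2 and 8.3). Calculation (b) falls below 366 at 2:1 and 3:1.
- *The omitted courses are the longest, so mean duration is biased down.* This is plausible but not shown. Many of these subjects had only vehicle before: at 2:1 in calculation (a), 200 × 0.895 = 179 of 423.

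It is also fair to say that changing how a period opens does not by itself give the never-responder a duration. Footnote 2 closes a period only at IGA-CHE 0/1, so the fix must cover closure too.

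**Conclusion.** The definition is wrong as written and should be corrected. Its literal effect is one on-treatment period too few for each subject entering with IGA-CHE ≥2, and none for those who never relapse. This carries into the number, rate and mean duration of on-treatment periods. Missed applications are affected if Section 14.3.3 uses the same definition. On-treatment days and the on/off split of AEs are affected only if they are derived from footnote 2.

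The consequence is limited. These outputs are exploratory and descriptive, and the trial makes no comparative analyses (Section 14.1). The primary AE count and all secondary endpoints do not use the definition.

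The affected group is probably more than half of the trial. At 2:1 it is about 423 under calculation (a) and 329 under (b). Both rest on phase 2b rates, obtained with an IGA-CHE since revised (Section 11.4.1), and on an assumed allocation. The documents give neither the allocation nor the response rate among roll-over subjects.

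**What to change.** In Panel 3, footnote 2:

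1. Replace 're-initiated' with 'initiated (at baseline or later) or re-initiated', so that a Day 1 start at IGA-CHE ≥2 opens period 1.
2. Add that, for analysis, a course that never reaches IGA-CHE 0/1 ends at the earliest of the Week 36 visit, discontinuation of IMP, initiation of rescue treatment or withdrawal from the trial.

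Apply the revised definition in Sections 14.3.3 and 14.3.6. Keep the Section 7.1 meaning of re-initiation only for the endpoint on time to response after re-initiation, where it is needed.

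The cost is a short wording change in the protocol or SAP. It alters the analysis definition only and leaves treatment rules as they are. No new data are needed, because Section 9.8.4 already has first and last application dates recorded for each start and stop.
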